8.1.4 Storage Conditions

The IMD devices are shipped as soon as they are produced because they are custom devices which are made to order. Therefore, they are not stored on any shelves. The conditions in which they should be shipped and kept by the end user are described in the IFU. They should not be exposed to temperatures below -25° and not above 60° Celsius.

8.2 Administration of experimental and control interventions

8.2.1 Experimental Intervention

The IMD is worn completely inside the ear canal. It is non-invasive. The amplification is prescribed based on the participant's hearing loss. The IMD will be worn by each participant for approximately 2 weeks to give the subjects enough time to wear the devices in different environments and make a comparison between the IMD and the RMD. Normal use of a hearing aid is 8-10 hours per day. The participants will wear the IMD for the same amount of time during the day that they wear the RMD. The hours of daily use will be controlled with a data logging feature in the software that programs the hearing aids.

The study procedure will use a single group assignment design in which the subjects will wear the IMD at the same time. As stated previously, the device is non-invasive and requires no surgical procedure. The device is inserted into the ear canal where it fits the subject's ear canal only as they are custom instruments and made from an impression of the subject's ear canal.

8.2.2 Control Intervention

The RMD is worn over the ear with a piece (earmold or dome) that is worn inside the ear canal. The RMD is the current marketed device. They will use the RMD programmed for the current study for approximately 10 +/- 7 days and then switch to the IMD. They will compare the IMD to the RMD after the 10-day field test with the IMD. Normal use of a hearing device is 8-10 hours per day. They will wear the RMD and the IMD for the same amount of time each day. The hours of daily use will be controlled with a data logging feature in the software that programs the hearing aids.

The study procedure will use a single group assignment design. The subjects will have already worn the RMD during the first period, and will then all wear the IMD at the same time during the second period. As stated previously, the device is non-invasive and requires no surgical procedure. The RMD device is placed over the ear and the dome or earmold is placed inside the ear canal. The subjects themselves will place the device in their ears each morning and remove them each night for sleeping. The test subjects are experienced users of the BTEs, same style as the RMD, and will have been placing it on their ears for at least 6 months before beginning the current study. They will have been given an Instructions for Use booklet when fitted with the devices that explains how to insert the device and provides further instructions concerning cleaning, battery changing, and warnings.

8.3 Device modifications

The IMD will provide the similar amplification as the RMD; therefore, the subject should not experience any significant negative differences that would make the subjects want to discontinue use of the device. However, if a subject does report such differences, that can be improved with fine tuning, fine tuning can be made to improve the situation enough for the subject to continue with the study. If the subject requests to discontinue they can immediately remove the IMD from their ear and return to using their own BTEs. They will be asked to return the IMD to Bernafon AG, but their data will still be included in the results for the current study. All data will remain encoded because the results are only recorded using the identification code of the subject.

8.4 Compliance with study intervention

It is clearly explained to the subjects that during the period of intervention it is important to the study that they only wear the RMD and IMD. However, their own BTEs are left in their possession for safety reasons in the event that they choose to discontinue their participation in the trial or a problem arises with the test devices. For ethical purposes, the subjects must have a back-up solution for their hearing impairment.

The data logging feature of the software monitors the average number of hours that the devices are worn each day. Therefore, it will be noted if the RMD and IMD have not been worn a standard or expected amount of time.

8.5 Data Collection and Follow-up for withdrawn participants

Any data that is collected will be kept in the data management database. The data will remain encoded because results are only recorded using the identification code of the subject. The analysis and report will include a section based on the data available from all recruited subjects (as the intention to treat ITT) and another section based on the data from the subjects that complete the entire protocol (per protocol PP). Withdrawn subjects will have the same follow-up as those subjects that complete the trial. As all subjects are taken from the Bernafon database, all participants, including those that withdraw, are welcome to return to the clinic for fine-tuning and maintenance as needed.

8.6 Trial specific preventive measures

The performance of a hearing aid is not impacted by medication. The subjects will continue to take whatever type of medication that they normally take. There will be no impact on the study objectives.

8.7 Concomitant Interventions (treatments)

Test subjects will continue to receive any concomitant care and medication that they normally receive during the trial. All test subjects will already be hearing aid users and will have, therefore, used them while receiving other types of care or medications. There will be no impact on the study objectives.

8.8 Medical Device Accountability

The RMD and IMD devices have serial numbers by which the individual device can be identified and the production history traced. The devices will be shipped from the production lab in Poland. The serial numbers will provide traceability of their production. All devices undergo testing in production before being shipped. Only IMD that are from a tested batch will be used in the study.

8.9 Return or Destruction of Medical Device

At the end of the study all of the subjects will return the IMD to the site in Bern. It will be noted in the device accountability log and CRF that the devices were returned.

The PI will then return the devices to the Sponsor.

9. STUDY ASSESSMENTS

9.1 Study flow table of study procedures and assessments

Study Periods	Intervention Period		
	Screening/1	2	3
Visit	0	10 +/- 7 days	20 +/- 5 days
Day	0	10 +/- 7 days	20 +/- 5 days
Patient Information and Consent	x		
Demographics	x		
Medical/Hearing History	x		
In-/Exclusion Criteria	x		
Randomization		x	x
Otoscopy	x	x	x
Audiometry	x		
Ear Impressions	x		
Administer Medical Device	x	x	
Primary Variable (speech testing)		x*	x*
Secondary Variables (APHAB)	x	x	
Secondary Variables (product questionnaire)	x	x	
Other Variables (preference questionnaire)			x
Adverse Events	x	x	x

*Randomization of lab trial test conditions

9.2 Assessments of outcomes

9.2.1 Assessment of primary outcome

The primary outcome is the objective speech testing results of the IMD compared with the RMD. Speech will be tested with the RMD and the IMD at the second and third appointments. Two speech tests, the OLSA and the GÖSA, will be used and with three conditions: unaided, aided with the RMD, and aided with the IMD.

9.2.2 Assessment of secondary outcomes

The overall performance of the IMD versus the RMD will be subjectively measured using a standardized questionnaire (APHAB) and two in-house questionnaires (product and preference). The subjects will rate the RMD using the APHAB and the IMD using the APHAB. The results from the two APHAB questionnaires will be compared. The product questionnaire will also be answered for both the RMD and IMD and the results compared. At the end of the trial the participants will be asked to complete a preference questionnaire where they shall choose either the RMD or the IMD as their preferred hearing aid and explain the reason for their choice.

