7.4 Criteria for withdrawal / discontinuation of participants

Participants are allowed to withdraw from the study at any time and for any reason. They do not have to share the reasons with the investigator. They will be asked to return the IMD. If the decision to withdraw is made by the investigator, the PI will inform the subject in person that they are no longer needed for the study. Reasons for withdrawing a participant from the study could be for non-compliance during testing, unreliable responses, medical reasons such as an ear infection, or the study may need to be stopped or postponed. Any data gathered from these subjects will be used for the current study. All data will remain encoded because results are only recorded using the identification code of the subject. There are normally at least five “back-up” test participants on the list to replace those that withdraw or are withdrawn. The “back-up” participants have already been screened and deemed to be appropriate for the study.

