9.2.4 Assessments in participants who prematurely stop the study

After the study concludes the subjects will return the IMD. The follow-up procedure will be the same as for all active test subjects. They will be instructed to return to the clinic for any required maintenance or fine-tuning of their own devices. Those that prematurely withdraw from the study will still be wearing their own devices; therefore, their follow-up treatment will be the same as for the other participants that finish the study.

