9.3.3 Final/Third Visit

Final Visit, Day 28 +/- 5: The subjects will return the completed questionnaires. They are randomized for the speech testing. Speech tests are made with the GÖSA in three conditions: unaided, aided with RMD, and aided with IMD. They return the IMD and can continue to use their own BTEs as normal. The subjects will complete a preference questionnaire to determine if they preferred the IMD or the RMD. They are notified that the study has ended. They are given their reimbursement and instructed to continue using the clinic at Bernafon for routine device maintenance. Any AEs are reported in the CRFs.

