11.5 Handling of missing data and drop-outs

For missing data, the PI will contact the involved subject to evaluate the possibility of getting missing data from a questionnaire by post. If a test subject cannot come to the evaluation visit, after exhausting all the possibilities to reschedule a new one, the devices will be sent back per post. If a subject does not want to adhere to the protocol, he can easily switch back to his own devices and return the IMD.

Dropouts will not be replaced; therefore, extra subjects over the calculated sample amount will be included from the beginning to ensure enough completed cases with all data.

The analysis and report will include two separate sections. The first section is based on data from all recruited subjects (as the intention to treat ITT part) and the second section is based on the data from subjects that complete the entire protocol (per protocol PP). Demographical and audiological data (e.g. hearing loss thresholds, degree, and classification) will be available from all recruited subjects including the withdrawn subjects and will be analysed in the report.

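### Preference is collected only at visit 3, with nothing arranged for subjects who stop the IMD early, so the preference share can rest on completers alone and can lean towards the IMD

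*Protocol*

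**What the plan says.** **Timing.** Section 9.2.2 states: "At the end of the trial the participants will be asked to complete a preference questionnaire where they shall choose either the RMD or the" investigational device (IMD). A reason is asked for along with the choice. The flow table in 9.1 lists "Other Variables (preference questionnaire") with a single mark, under visit 3. Section 9.3.3 agrees: "The subjects will complete a preference questionnaire to determine if they preferred the IMD or the RMD". Sections 5.2 and 9.2.2 treat preference as a secondary outcome; the flow table files it under other variables.

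**Ways out before visit 3.** On dissatisfaction with the device, 8.3 says: "If the subject requests to discontinue they can immediately remove the IMD from their ear and return to using their own BTEs". Section 10.1 has subjects withdrawn when pain prevents use. Section 7.4 allows withdrawal by the subject for any reason, or by the investigator.

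**What early stoppers get.** Section 9.2.4 says: "The follow-up procedure will be the same as for all active test subjects". It goes on to describe maintenance and fine-tuning of the subject's own aids and names no questionnaire. Section 11.5 has the investigator explore whether missing questionnaire data can be obtained by post, and has the devices posted back if a subject cannot attend.

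**What is reported.** Sections 8.5 and 11.5 require one section on all recruited subjects and one on those who complete the protocol. Sections 7.4, 8.3 and 8.5 keep withdrawn subjects' data. Section 10.1 gives removal of partial data as one purpose of a pain withdrawal.

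**The concern.** An answer to this item exists only for people who are still in the study at the last visit. Two of the exits, requested discontinuation and pain, follow from experience with the IMD. Subjects who like the IMD least may therefore be the least likely to be asked. If so, missingness is related to the answer, and the share preferring the IMD is too high.

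Keeping data already gathered does not help, because no preference answer has been gathered at that point. The section on all recruited subjects would then carry a completer-only figure under an intention-to-treat label. The synopsis gives end-user satisfaction with the ITE devices as something the study should validate, and early rejection of the ITE style bears directly on that.

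**Working it through.** **1. Which forms can be recovered by post?** By 9.3.1 and 9.3.2, the APHAB and product questionnaires are handed out at visits 1 and 2 for completion at home. A subject who stops the IMD between visits 2 and 3 already holds those two forms, so postal retrieval fits them. The preference form is first given at visit 3 (9.3.3), so this subject does not hold it. Section 11.5 does not say that a form not yet issued will be sent.

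**2. The plan's own figure.** No number is stated for preference. The only computed size is for the OLSA comparison (11.2): n = (σ(z₀.₉₅ + z₀.₈₀)/δ)² = (1.6 × (1.645 + 0.842)/1)² = 15.83, rounded up to 16. This reproduces the stated 16. It matters here only because 6.1 plans about 20 subjects (the synopsis says 15–20) and 11.5 explains the surplus: "extra subjects over the calculated sample amount will be included from the beginning to ensure enough completed cases with all data". With 20 enrolled and 16 needed there is room for 4 losses. That is room, not a forecast, since no dropout rate is given.

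**3. Size of a possible tilt.** Let N be enrolled, d the early stoppers without an answer, and k the number choosing the IMD, all of them among completers. The completer share is k/(N − d) and the all-enrolled share is k/N.

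Assumptions, none of them in the protocol: k = N/2, and none of the d stoppers would have chosen the IMD.

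| d | N = 20 | N = 16 |
|---|---|---|
| 0 | 10/20 = 50.0% | 8/16 = 50.0% |
| 1 | 10/19 = 52.6% | 8/15 = 53.3% |
| 2 | 10/18 = 55.6% | 8/14 = 57.1% |
| 3 | 10/17 = 58.8% | 8/13 = 61.5% |
| 4 | 10/16 = 62.5% | 8/12 = 66.7% |

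The all-enrolled share is 50% in every row. The shift starts near 3 points for one unscored stopper and reaches 12.5 points for 4 of 20. For scale, the standard error of 10/16 is √(0.625 × 0.375/16) = 0.121, or 12.1 points.

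**4. Direction.** If the 4 without an answer would all have chosen the IMD, the same 10/16 would compare with 14/20 = 70%. The tilt towards the IMD depends on why subjects leave, which the plan cannot show in advance.

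**The case against.** **Early stoppers are not necessarily lost.** Section 11.5 seeks missing questionnaires by post, 8.3 keeps discontinuers' data, and 8.5 and 11.5 require a section on all recruited subjects. This stands against any claim that early stoppers are never scored or that the result is biased as a matter of fact. It does not remove the gap, because postal contact is only an attempt and the preference form has not been issued by then.

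**Giving up the IMD is not a vote for the RMD.** A reader might infer that a subject who returns the IMD has already shown a preference and should be counted against it. The documents do not support this. By 8.3 the subject goes back to their own BTEs. By 9.3.2 the RMD was handed in at visit 2, and the question is RMD against IMD. Section 6.2.3 itself recognises that subjects may favour their previous BTE fitting. Section 7.4 also lists exits that need not concern preference, such as ear infection, unreliable responses, or the study being stopped. This objection stands in full and rules out such scoring as the main result.

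**The counting rule may sit in an SAP.** That is fair for the treatment of missing answers. It does not cover when the form is given, which the protocol fixes.

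**The magnitude can be overstated.** A reader might cite 12/16 = 75% against 12/20 = 60% (one-sided sign tests p = 0.038 and p = 0.25) as a lost significant result. The protocol plans no test of preference. Nor can the back-up list in 7.4 ("There are normally at least five “back-up” test participants on the list to replace those that withdraw or are withdrawn") be added to the possible losses: those people are replacements, and 11.5 says dropouts are not replaced.

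**The two-option format.** It might be blamed for the tilt, but it plays no part in who is missing, and the questionnaire itself is not shown.

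**Conclusion.** The point holds in a limited form. Preference is scheduled once, at visit 3. The protocol arranges no preference assessment for subjects who stop the IMD earlier, and some of them would stop because of the IMD. The reported share can therefore be completer-only, even in the all-recruited section, and can lean towards the IMD.

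The 12.5-point figure is an illustration that assumes 4 of 20 subjects stop, all because of the IMD, and that none of their answers is recovered. The effect is zero if nobody stops early or if the answers are obtained.

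The importance is minor. Preference is a secondary or other item with no test, margin or success criterion, and the primary OLSA comparison, measured at visit 2, is not touched.

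**What to change.** - **9.2.2 and 9.2.4:** give the preference questionnaire, with its reason item, when the IMD is handed back, at visit 3 or earlier. If the device comes back by post, send the form as part of that return.
- **Report:** in the all-recruited section, show these answers beside the completer share, and state how many early returners have no answer.
- **Sensitivity only:** counting unanswered early returners as not preferring the IMD may be shown as a worst-case bound, labelled as such, and not as the main figure.
- **Reconcile:** 7.4, 8.3 and 8.5 keep withdrawn subjects' data, while 10.1 speaks of removing partial data after a pain withdrawal. The protocol should state one position, because it decides whether these subjects appear in the all-recruited section.

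The cost is a few sentences, one extra form for each early stopper and one more line in the results table. The IMD share may come out less favourable.

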9.2.3 Assessment of safety outcomes

The product questionnaire will specifically ask questions about safety and unexpected noises/behaviour of the instruments. Unexpected behaviour includes unprovoked feedback, distorted sounds or artefacts, discomfort, spontaneous muting or shutting off, unexplained warning signals or beeps, and loud sounds. This information provided from the subjects will alert the PI about any potential for safety risks that should be addressed before the product is released to the market. It is not expected that any of these things will occur and have not during testing on previous products.

9.2.3.1 Adverse events

For the recording of adverse events the subjects will be asked for a description of the event including how long it lasted, how many times it occurred, and if it caused discomfort or pain or a disruption of hearing ability. They will be recorded on the AE forms in the CRF.

9.2.3.2 Laboratory parameters

Not applicable

9.2.3.3 Vital signs

Not applicable

9.2.4 Assessments in participants who prematurely stop the study

After the study concludes the subjects will return the IMD. The follow-up procedure will be the same as for all active test subjects. They will be instructed to return to the clinic for any required maintenance or fine-tuning of their own devices. Those that prematurely withdraw from the study will still be wearing their own devices; therefore, their follow-up treatment will be the same as for the other participants that finish the study.

9.3 Procedures at each visit

9.3.1 Screening/First Visit

Screening visit, Day 0: The potential participants will be given the Patient Information and Informed Consent form. The trial will be explained including how many visits are expected as well as the type of testing that they will complete. They are given time during the appointment to decide whether to participate in the study. If they choose not to take part in the study they will not sign the consent form, and the appointment will finish. If they choose to join the trial they will sign and date the consent form. No trial activities will be performed before the consent form is signed and dated by the subject and the investigator. Subjects will receive a copy of the signed consent form. A hearing history is then taken and otoscopy is performed. A hearing test is performed and inclusion/exclusion criteria will be determined. An ear impression is taken of each ear to create the IMD, and the RMD programmed to a first fit and adjusted using REM data in order to better match the electroacoustic output of the RMD and the IMD. They are given two questionnaires (APHAB and product) to complete at home regarding

the RMD. They are scheduled for the second visit. Any AEs are reported in the CRFs.

9.3.2 Fitting/Second Visit

Fitting Visit, Day 10 +/-7: Otoscopy is performed, and the subjects are fitted with the IMD. Output of the IMD is measured, and the fitting adjusted, if necessary, to better match the electroacoustic output of the previously worn, RMD. They are randomized for the speech testing. Speech tests are made with the OLSA in three conditions: unaided, aided with RMD, and aided with IMD. The subjects return the RMD and held until the third appointment for further speech testing. The subjects return the completed questionnaires from the first visit and are given two more questionnaires (APHAB and product) to complete at home. They are given instructions about the IMD and an IFU with information about the IMD. They are scheduled for the third visit. Any AEs are reported in the CRFs.

9.3.3 Final/Third Visit

Final Visit, Day 28 +/- 5: The subjects will return the completed questionnaires. They are randomized for the speech testing. Speech tests are made with the GÖSA in three conditions: unaided, aided with RMD, and aided with IMD. They return the IMD and can continue to use their own BTEs as normal. The subjects will complete a preference questionnaire to determine if they preferred the IMD or the RMD. They are notified that the study has ended. They are given their reimbursement and instructed to continue using the clinic at Bernafon for routine device maintenance. Any AEs are reported in the CRFs.

